3.1 Primary Outcomes

The following primary quantitative outcome measures for the trial will be assessed for the grant deliverables:

- (1) **Change in caregiver burden at 8 weeks and 6 months.** Self-reported caregiver burden will be assessed by the Disruption subscale on the Revised Memory and Behavior Problem Checklist (RMBPC) questionnaire. The range in subscale scores is 0 to 32 with higher scores representing a worse outcome.

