7.2.6 Effect of STAR-VTF on CG burden and PLWD antipsychotic medication use.

We will measure overall caregiver burden using the Revised Memory and Problem Behavior Checklist (RMPBC). We will use GEE with a working correlation matrix to estimate the regression model, using robust sandwich estimators to calculate standard errors accounting for within person correlation. We will adjust for baseline pre-randomization covariates: PLWD stage of dementia (DSRS), PLWD FAQ score, PLWD age and sex, caregiver relationship (spouse, non-spouse), caregiver age and sex, and caregiver highest level of education attained.

We will use generalized estimating equations (GEE) with a working correlation matrix to estimate a logistic regression model for refill (versus no refill) of the initial antipsychotic medication. Models will be adjusted for PLWD stage of dementia (DSRS), PLWD FAQ score, PLWD age and sex, caregiver relationship (spouse, non-spouse), caregiver age and sex, and caregiver highest level of education attained, study arm. We will again use GEE with a working correlation matrix to estimate a logistic regression model for daily versus “less than daily” use of antipsychotic medication (as reported to the coach). Models will again be adjusted for pre-randomization variables listed above.

7.2.7 Caregiver depression, stress and self-efficacy.

Caregiver depression will be measured using the PHQ-8. Caregiver self-efficacy will be measured using the Caregiver Mastery Scale. Caregiver stress will be measured using the Kingston Caregiver Stress Scale. We will again use GEE to compare the mean PHQ-8, CMS and Kingston scores in the STAR-VTF and attention control arms. Models will be adjusted for pre-randomization variables as above.

7.3 *Handling of Missing Data*

Preventing missing data is superior to statistical treatment. We will make every effort to collect data on all study participants. If there are substantial missing data or significant loss-to-follow-up, we will use inverse probability weighting(23) to rebalance the STAR-VTF and attention control group. Inverse probability weights are used to rebalance groups on prognostic factors when the treatment and control groups become unbalanced over time, post-randomization, due to study drop out. If we find intermittent missing data, we will instead use multiple imputation(24) via chained equations to address the problem, using at least 10 imputed datasets and combining results using Rubin's rules.

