STAR Caregivers – Virtual Training and Follow-up

Grant Number: 1 R01AG061926-01

Principal Investigator: [name]

STATISTICAL ANALYSIS PLAN

Background/overview/purpose of study:

This is a randomized trial that tests whether receipt of telehealth training for caregivers of people with dementia can reduce utilization of antipsychotic medications, as well as improve the living conditions of both the caregiver as well as the person with dementia.

Scientific questions and outcomes:

1. Is there a change in the rate of antipsychotic medication fills within eight weeks, comparing the intervention to the control arm
 - a. Main measures: Any fill within eight weeks (binary), any refill within eight weeks (binary)
2. Is there a change in standardized scales of caregiver mastery as well as dementia symptoms.
 - a. Primary scales: Revised Memory Problem and Behavior Checklist, Caregiver Mastery, Kingston Caregiver Stress
 - b. Secondary analyses: Dementia Severity Rating Scale subscales

Predictors of interest (independent variable, could be just treatment groups, indicate type as in outcome of interest section):

All analyses will adjust for gender and age, as well as the baseline score. (e.g. the caregiver mastery analysis will adjust for caregiver mastery at baseline) Our variable of interest will be the randomization group.

Unit of analysis:

The dyad of the caregiver and person with dementia.

Other data/analytic specifics (e.g. subgroups of interest, brief discussion of missing data):

Subgroups will be exploratory analyses; we are not specifically powered on any. Missing data will be accounted for via multiple imputation via chained equations, using 100 imputed datasets.

Analytic approach, special Issues and proposed sensitivity analyses:

This is a straightforward randomized trial, so analyses will be run using ordinary least squares regression with empirical standard errors for continuous outcomes, and logistic regression for binomial outcomes. Rubin's Rules will be used to combine results across the multiple imputation datasets.

Analytic software (and version if known):

Stata, version 17.0

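### The protocol has one primary outcome, but the SAP lists three primary scales with no subscale or visit, and neither document says how the 8-week and 6-month results decide H1

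*SAP*

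**What the plan says.** Protocol 3.1 lists a single primary outcome: "Change in caregiver burden at 8 weeks and 6 months". It fixes the instrument ("Self-reported caregiver burden will be assessed by the Disruption subscale" of the RMBPC) and the scale ("The range in subscale scores is 0 to 32"). H1 under AIM 3 names the same two time points. AIM 3 and section 3.2 both place caregiver stress (Kingston scale) and self-efficacy (Caregiver Mastery Scale) among the secondary outcomes. Section 7.1.1 calls the RMBPC the primary outcome and derives 39 dyads per arm from d = 0.65, type-I error 0.05 and 80% power.

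Two later places do not carry this through. Section 7.2.6 reads "We will measure overall caregiver burden using the Revised Memory and Problem Behavior Checklist", without the subscale, and plans GEE with robust standard errors for within-person correlation, without naming an arm-by-visit term or a contrast. The SAP's second question is "Is there a change in standardized scales of caregiver mastery as well as dementia symptoms". Beneath it stand "Primary scales: Revised Memory Problem and Behavior Checklist, Caregiver Mastery, Kingston Caregiver Stress" and, one tier down, "Secondary analyses: Dementia Severity Rating Scale subscales". No visit is given for any of these scales; the SAP's only time point, eight weeks, belongs to medication fills. The SAP's model for continuous outcomes is ordinary least squares, and "All analyses will adjust for gender and age, as well as the baseline score".

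**The concern.** Someone working from the SAP would put three scales in the top tier, where the protocol has one, and would not find which RMBPC score or which visit to analyse. Someone working from the protocol would know the score and the visits, but not what pattern of results supports H1.

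The models do not fill the gap. A GEE over both visits could give one pooled arm effect or two visit-specific effects, and no contrast is named. An ordinary least squares model takes one outcome per dyad, and no visit is named. The sample size covers one test at the full 0.05. Depending on the rule eventually used, the trial could claim success at more than the 5% error rate, or hold 5% with less power than the protocol states.

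**Working it through.** **Inputs from the documents.** d = 0.65, type-I error 0.05, power 80%, equal arms, 39 per arm (7.1.1); up to 90 dyads retained at 6 months, so at most 45 per arm (7.1). **Assumed, because the documents do not give them:** two-sided testing, the correlation between visits (0.5 to 0.8) and the correlation between scales (0 to 0.8).

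**1. The plan's own figure.** Two-sample t-test with 2n - 2 degrees of freedom and noncentrality d x sqrt(n/2). At n = 39 this is 0.65 x sqrt(19.5) = 2.87. Power is 79.9% at 38 and 80.9% at 39 per arm (exact solution 38.14); a one-sided test would need about 30. So 39 per arm is one two-sided test at 0.05. Inflation: 39 x 1.3 = 50.7, stated as 50. Power at 45 per arm is 86.2%. The arithmetic is sound for one test.

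**2. Error rate if any one success counts.** For k independent tests it is 1 - 0.95^k. For correlated tests I used 2,000,000 multivariate normal draws under the null, counting any |Z| > 1.96.

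| Tests | Assumed correlation | Family-wise error |
|---|---|---|
| RMBPC, two visits | 0.5 / 0.8 between visits | 9.1% / 7.8% |
| Three scales, one visit | 0 / 0.5 / 0.8 between scales | 14.3% / 12.5% / 9.8% |
| Three scales, two visits, 0.5 between visits | 0 / 0.3 / 0.5 / 0.8 between scales | 24.8% / 23.8% / 22.0% / 17.3% |
| Three scales, two visits, 0.8 between visits | 0 / 0.3 / 0.5 / 0.8 between scales | 21.7% / 20.6% / 19.0% / 14.9% |

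The first entry of the second row is exact: 1 - 0.95^3 = 0.1426. The 25% end needs three scales completed by the same caregiver to be uncorrelated; at 0.3 to 0.5 between scales the range is 19-24%.

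**3. Power of each possible rule for the two visits.** RMBPC only, unadjusted for baseline, 39 per arm, d = 0.65 at both visits (which 7.1.1 does not state), between-visit correlation r from 0.5 to 0.8:

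- Single named visit, or first step of a fixed sequence: 80.9%.
- Both visits required, each at 0.05: about 70-74% (about 77-81% at 45 per arm). Alpha is not inflated.
- Holm, success at one or more visits: 80-86%. Holm, success at a given visit: 76-78%.
- One pooled arm effect. The mean of the two visits has standardised effect [(d1 + d2)/2] / sqrt[(1 + r)/2]. With 0.65 at both visits this is 0.65/sqrt(0.75) = 0.751 at r = 0.5 and 0.65/sqrt(0.90) = 0.685 at r = 0.8, so power is 85-91%.
- Pooled, if the effect wanes to d = 0.5 at 6 months (assumed). The mean effect is 0.575, giving 0.575/sqrt(0.75) = 0.664 and 0.575/sqrt(0.90) = 0.606, so power is 75-83%.

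**4. Baseline adjustment.** If d is on the unadjusted scale and the baseline-outcome correlation is 0.5 (assumed), the SAP's adjustment raises single-visit power at 39 per arm to about 90% and both-required power to 82-85%. The shortfall under the both-required rule therefore depends on a correlation that the plan does not give.

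**The case against.** The strongest reply is that section 3.1 already settles the matter. It fixes the questionnaire, subscale, range and visits; 7.1.1 calls the RMBPC the primary outcome; AIM 3 and 3.2 place stress and self-efficacy as secondary. On that view the SAP's label only ranks scales within its second question, above the dementia severity subscales, and the wording in 7.2.6 simply names the parent questionnaire. The word joining the two visits in 3.1 and H1 may also mean that both are required, which would protect alpha. The within-person correlation in 7.2.6 could equally point to one joint model and a pooled effect.

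Much of this stands. The wording in 7.2.6 is ambiguous rather than contradictory. A reader might infer that the scale and subscale are open to choice once the data are seen; the documents do not support that, because 3.1 fixes both. Nor does the blinding section strengthen the point: it un-blinds the biostatistician when preparing Safety Officer reports, but does not say that those reports compare burden, mastery or stress by arm.

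What remains is that the SAP does not say its label is local, and that the both-required and pooled readings are each possible but neither is stated. They are different tests with different power.

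**Conclusion.** The point holds and should be corrected before any outcome comparison by arm. The SAP's top tier contradicts Protocol 3.1, AIM 3 and 3.2, and the rule for the two visits is absent from both documents.

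The size depends on the rule eventually read into the plan. Error rates of about 8-9%, 10-14% or 15-25% arise only if any one success counts, and rest on assumed correlations. It would be wrong to conclude that the trial runs at a 25% error rate, since neither document adopts that rule. If both visits are required, the 5% rate holds and the cost is power: about 70-74% unadjusted at 39 per arm, assuming d = 0.65 at both visits. Nor is the sample size calculation in error. It covers a single test, and the plan does not say which one.

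**What to change.** - **SAP and 7.2.6:** name the RMBPC Disruption subscale as the sole primary outcome, as in 3.1. List Mastery and Kingston as secondary, as in AIM 3 and 3.2.
- **Rule for the visits:** before any outcome comparison by arm, state one of: a single primary visit; a fixed sequence; both required, each at 0.05; one pooled arm effect; or Holm. For Holm, say whether success means one or more visits or a given visit.
- **Model:** plan the same model, GEE or ordinary least squares, in both documents, and name the contrast so that it estimates what the rule tests.
- **Section 7.1.1:** say which RMBPC score and which visit d = 0.65 refers to. Restate power for the chosen rule unless it is a single visit or the first step of a sequence. The pooled rule is not exempt, because its power depends on the effect at both visits. Give the assumed between-visit and baseline correlations and the retention.

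The cost is mainly wording. A single visit or the first step of a sequence keeps the present 39 per arm. Mastery and Kingston lose primary status, and the stated power may become slightly less favourable under some rules. In a fixed sequence the second visit can be claimed only after the first succeeds, and a pooled test supports no separate claim by visit.

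Antipsychotic use also differs between the documents in tier and window (H2 at 6 months, secondary in 3.2, an eight-week main measure in the SAP). That should be reconciled as a separate point.

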AIM 3: Test the hypotheses that (H1) caregiver participants in STAR-VTF will have lower levels of caregiver burden at 8 weeks and 6 months compared to an attention control group; and (H2) PLWD participants in STAR-VTF will have lower rates of antipsychotic medication use at 6 months compared to control. Secondary outcomes are: caregiver depression, caregiver stress and caregiver self-efficacy. We propose to recruit 100 CG-PLWD dyads (50 per arm).

This will be the first study to test a low intensity, self-directed caregiver training program with remote support from social workers. It will also be the first study to measure changes in antipsychotic medication use by PLWD after CG training. Kaiser Permanente is an ideal setting because we have access to the complete EHR, prescription medication use, health care use, and demographic data. We will be able to identify and enroll participants in real-time using an automated data algorithm as we have done previously.(22) This study will be an important step in expanding access to training and support in a format that could be implemented within integrated delivery systems with capitated payments (i.e., Accountable Care Organizations). Growing use of EHR portals in these organizations will further increase demand for web-based care management/support. Demand will also increase as today's near-retirees, familiar with web-based applications, develop ADRD. Kaiser Permanente has pioneered such efforts and is the lead site in the Mental Health Research Network (MHRN). Findings from this study will inform a future multi-site pragmatic trial across the 13 health systems and 12 million enrollees in the MHRN.

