3.2 Secondary Outcomes

The following secondary outcome measures for the trial will be assessed:

- (1) **Antipsychotic medication Use.** Proportion of participants will at least one antipsychotic prescription refill after initial medication dispensing, using automated system pharmacy data.
- (2) **Change in caregiver depression.** Self-reported caregiver depression assessed by the 8-item Patient Health Questionnaire (PHQ-8). The PHQ-8 is an eight-item measure of depression that assesses symptoms over the last two weeks. The total sum of the 8 responses from the PHQ-8 ranges between 0 and 24 with higher scores indicating worse outcome. In general, a total of 10 or above is suggestive of the presence of depression.
- (3) **Change in caregiver self-efficacy.** Self-reported caregiver self-efficacy assessed by the Caregiver Mastery Scale. Total scores can range from 7 to 35, with higher scores reflecting greater caregiver mastery. The Caregiver Mastery Scale is a 7-item measure of self-efficacy. is a 7-item self-report scale, indicating the extent to which respondents agree (5) or disagree (1) with each item. Three items with negative statements are reverse-scored. Total scores can range from 7 to 35, with higher scores reflecting greater caregiver mastery.
- (4) **Change in caregiver stress.** Caregiver stress will be measured on the Kingston Caregiver Stress Scale. This is a 10-item measure with respondents rating the level of stress between 1 (coping fine, no stress) to 5 (extreme stress, feeling at the end of rope). Total scores vary between 10 and 50.
- (5) **Response rates for baseline, 8-week, and 6-month measures.** We will assess participants' willingness to complete study measures using the REDCap online survey by the proportion completing study measures at each time point.
- (6) **Training Completion rate.** We will report training completion rates as a measure of feasibility. Completion will be defined as viewing all 6 online training modules, conducting at least 3 phone calls with a study coach and sending at least one secure message to a study coach in the baseline to 8-week period and one message in weeks 9 through 24.
- (7) **Primary care visit rates.** Measured as the number of primary care visits per eligible study participant during the study period.

- (8) **Urgent care visit rates.** Measured as the number of urgent care visits per eligible study participant during the study period.

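### The SAP leaves out the PHQ-8 depression outcome, so its only planned model has no baseline PHQ-8, and it adds DSRS subscales that the protocol never lists as an outcome

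*SAP*

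**What the plan says.** **PHQ-8 in the protocol.** AIM 3 (section 2.2) states: "Secondary outcomes are: caregiver depression, caregiver stress and caregiver self-efficacy". Section 3.2(2) defines the depression outcome as a change: "Self-reported caregiver depression assessed by the 8-item Patient Health Questionnaire (PHQ-8"). Section 7.2.7 gives the model: "We will again use GEE to compare the mean PHQ-8, CMS and Kingston scores in the STAR-VTF and attention control arms". For covariates it adds only: "Models will be adjusted for pre-randomization variables as above". The list it points back to is in 7.2.6 and begins: "We will adjust for baseline pre-randomization covariates: PLWD stage of dementia (DSRS), PLWD FAQ score, PLWD age and sex, caregiver relationship (spouse, non-spouse"). It goes on to caregiver age, sex and education. No baseline outcome score is in it.

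**PHQ-8 in the SAP.** Question 2 names three scales: "Primary scales: Revised Memory Problem and Behavior Checklist, Caregiver Mastery, Kingston Caregiver Stress". Neither PHQ-8 nor depression appears anywhere in the SAP. Its adjustment rule is: "All analyses will adjust for gender and age, as well as the baseline score".

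**DSRS.** Directly under the primary scales the SAP lists: "Secondary analyses: Dementia Severity Rating Scale subscales". In the protocol the DSRS appears in the abbreviation list and as an adjustment covariate in 7.2.2, 7.2.3, 7.2.5 and 7.2.6 (and through 7.2.6 in 7.2.7). Sections 3.1 and 3.2 do not list it as an outcome, and its subscales are never mentioned.

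**The concern.** Depression, stress and self-efficacy are treated as a set in the protocol. The SAP keeps stress and mastery, drops depression without giving a reason, and brings in subscales of an instrument that was a covariate.

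This has two consequences. First, PHQ-8 would be analysed differently from the two scales it was grouped with: GEE instead of OLS, a different covariate set, no baseline score, and the protocol's missing-data rules (7.3) instead of the SAP's 100 imputed datasets. The baseline score is usually the strongest single predictor of a follow-up scale score, so omitting it can cost precision. Second, when one listed outcome is absent and an unlisted group is present, a reader of the results cannot tell which secondary findings were planned. The SAP does not say which DSRS subscales are meant, at which time point, or how several results will be interpreted.

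**Working it through.** **1. The plan's own figure.** Protocol 7.1.1 asks for 39 dyads per arm at d = 0.65, type I error 0.05 and 80% power. Taking the test as two-sided, the two-sample t calculation gives 38.14, rounded up to 39, so the figure reproduces. It concerns the RMBPC. No sample size or power is stated for PHQ-8 or the DSRS, and nothing below depends on it.

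**2. The lists side by side.**

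| Measure | Protocol role | SAP role | Baseline score in 7.2.6/7.2.7 list | Baseline score in SAP model |
|---|---|---|---|---|
| RMBPC | Primary (3.1) | Primary scale | No | Yes |
| Caregiver Mastery | Secondary (3.2(3)) | Primary scale | No | Yes |
| Kingston stress | Secondary (3.2(4)) | Primary scale | No | Yes |
| PHQ-8 | Secondary (3.2(2)) | Not listed | No | Not reached |
| DSRS subscales | Not an outcome; DSRS is a covariate | Secondary analysis | Not applicable | Yes |

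PHQ-8 is the only one of the four caregiver scales with no baseline-adjusted analysis in either document.

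**3. Is baseline PHQ-8 available?** Section 7.2 says that measures are collected at baseline, 8 weeks and 6 months, and 3.2(2) defines the outcome as a change, which needs a baseline value. No new data collection is required.

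**4. Illustrative size.** The documents give no PHQ-8 standard deviation, effect size or baseline to follow-up correlation r. I assume r = 0.3, 0.5 and 0.7, and equal variance at both visits. Per-person outcome variances, in units of the follow-up variance, are:

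- follow-up score, unadjusted: 1
- change score: 2(1 − r)
- follow-up score adjusted for baseline: 1 − r²

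The SE ratio is √(1 − r²) against the unadjusted follow-up score. Against the change score it is √[(1 − r²) / (2(1 − r))] = √[(1 + r)/2].

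| r | Against unadjusted follow-up | SE cut | Against change score | SE cut |
|---|---|---|---|---|
| 0.3 | √0.91 = 0.954 | about 5% | √0.65 = 0.806 | about 19% |
| 0.5 | √0.75 = 0.866 | about 13% | √0.75 = 0.866 | about 13% |
| 0.7 | √0.51 = 0.714 | about 29% | √0.85 = 0.922 | about 8% |

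**5. The same in detectable effects.** Section 7.1 expects up to 90 dyads at 6 months, or 45 per arm. The effect detectable with 80% power is (1.96 + 0.84) × √[2(1 − r²)/45]. That is d = 0.59 without the baseline score, and 0.56, 0.51 and 0.42 with it at r = 0.3, 0.5 and 0.7. The 7.2.6 list has eight other covariates. Any variance they already explain reduces the gain over the unadjusted comparison.

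**The case against.** The strongest reply is that this is one missing list entry, not a choice of an inferior model. Within the protocol, PHQ-8 has the same model as Mastery and Kingston, and 7.2.6 names no baseline RMBPC for the primary outcome either. The SAP rule is worded to cover all analyses, so listing PHQ-8 would bring it in. That is correct, and it shapes the fix: the gap in the protocol covariate list is general and should be closed for every scale.

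It can also be said that the baseline is already used, because the outcome is defined as a change, or because the GEE might include the baseline visit as a repeated measure. The text allows this but does not state it; 7.2.7 speaks of comparing means. On a change-score reading the gain at r = 0.7 is about 8%, not 29%. Depending on how a GEE with the baseline visit were set up, it could be smaller still. The range must therefore be read across both columns of the table.

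On the DSRS, SAP question 2 does ask about dementia symptoms, and it places the subscales below the primary scales. The SAP states no time point or multiplicity rule for any scale in that question. What stands is that for the other scales the protocol's section 3 supplies an outcome definition, and for DSRS subscales it supplies none.

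Three stronger readings are tempting, and the documents do not support them:

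- *That depression gets the least precise analysis in the plan, with a large power loss.* A power figure needs an effect size for PHQ-8, and none is given. The comparator is also a covariate-adjusted GEE, not an unadjusted t-test.
- *That the DSRS subscales carry a false-positive risk near one half.* For 12 independent tests, 1 − 0.95¹² = 46%. But the number of subscales is not given, and subscales of one instrument are correlated. With an assumed pairwise correlation of 0.5 to 0.7, simulation for 12 tests gives about 32% to 23%.
- *That the omission signals selective reporting.* The documents show a mismatch and nothing about intent.

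**Conclusion.** The point holds as a mismatch between the documents with a modest analytic consequence. PHQ-8, a stated secondary outcome, is absent from the SAP and is left with a model that does not name its baseline score. DSRS subscales are an analysed outcome in the SAP and only a covariate instrument in the protocol. Both facts rest on the text alone.

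The precision figures (SE lower by about 5% to 29%, or 19% to 8%, depending on the comparator) rest on assumed correlations and equal variances. They show that adding the covariate is worthwhile on either reading, but they do not measure a loss in this trial. The PHQ-8 omission and the DSRS addition touch secondary outcomes only; neither affects the primary outcome.

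**What to change.** 1. In SAP question 2, add PHQ-8 as a secondary scale at 8 weeks and 6 months, under the same OLS model and imputation as Mastery and Kingston, adjusted for baseline PHQ-8.
2. In protocol 7.2.6 and 7.2.7, add the baseline score of each caregiver scale to the covariates, and state that the SAP model governs. Without that statement PHQ-8 would have both an OLS and a GEE model. Adding the baseline for PHQ-8 alone would leave RMBPC, Mastery and Kingston without theirs in the protocol.
3. Label the DSRS subscales exploratory in the SAP, name them and their time point, and report estimates with intervals. Listing them in protocol section 3, or removing them from the SAP, would also reconcile the documents.

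The cost is a few lines in each document, and the PHQ-8 data are already planned. The one thing given up is that, if labelled exploratory, a DSRS subscale result could not be presented as confirmatory. The change should be dated before outcomes by arm are examined.

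### For primary caregiver burden, the protocol and the SAP adjust for different covariates, only the SAP lists the baseline score, and neither says which model governs

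*SAP*

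**What the plan says.** **Protocol.** Section 3.1 makes the primary outcome "Change in caregiver burden at 8 weeks and 6 months", measured on the RMBPC Disruption subscale. Hypothesis H1 in section 2.2 is worded as a level: "caregiver participants in STAR-VTF will have lower levels of caregiver burden at 8 weeks and 6 months compared to an attention control group". Section 7.2.6 says "We will measure overall caregiver burden using the Revised Memory and Problem Behavior Checklist (RMPBC") and names no subscale. The model is: "We will use GEE with a working correlation matrix to estimate the regression model, using robust sandwich estimators to calculate standard errors". The covariate sentence begins "We will adjust for baseline pre-randomization covariates: PLWD stage of dementia (DSRS), PLWD FAQ score, PLWD age and sex, caregiver relationship (spouse, non-spouse") and goes on to caregiver age, sex and education. Baseline RMBPC does not appear in it.

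**SAP.** The checklist is one of three: "Primary scales: Revised Memory Problem and Behavior Checklist, Caregiver Mastery, Kingston Caregiver Stress". No subscale or time point is given for these scales. The model is "ordinary least squares regression with empirical standard errors for continuous outcomes, and logistic regression for binomial outcomes". On covariates: "All analyses will adjust for gender and age, as well as the baseline score". The unit of analysis is the dyad, and the SAP does not say which member's gender and age are meant.

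**Precedence.** Protocol 7.2.1, although headed as the statistical analysis plan, states only intention-to-treat and does not point to a separate SAP. The SAP neither cites protocol 7.2.6 nor says that it replaces it.

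**The concern.** An analyst cannot follow both documents for the same primary outcome. The SAP rule covers all analyses, so it is not an optional addition to the protocol list, and it leaves out DSRS, FAQ, relationship and education. The protocol list leaves out the baseline value of the outcome, which is usually the strongest predictor of the follow-up value.

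The stake is that two prespecified estimates and two p-values for the primary outcome can be taken from the same data, and the documents do not say which is the trial's result. Leaving baseline out of a raw-score model also costs precision.

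**Working it through.** **1. The plan's own figure.** Protocol 7.1.1 uses d = 0.65, type I error 0.05, power 80% and equal arms. The normal approximation gives 2 x (1.960 + 0.842)^2 / 0.65^2 = 37.2, so 38 per arm. The two-sided t-test gives 38.14, so 39, as stated. Inflation: 39 x 1.30 = 50.7, against 50 stated. The figure reproduces. It is an unadjusted two-group calculation, so it uses neither planned model and does not show which was intended.

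**2. The two plans side by side.**

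| Item | Protocol | SAP |
|---|---|---|
| Outcome | Disruption subscale (3.1); overall burden (7.2.6) | Checklist, no subscale |
| Time points | 8 weeks and 6 months (3.1) | None given for the scales |
| Model | GEE, sandwich standard errors | OLS, empirical standard errors |
| Covariates | DSRS, FAQ, PLWD age, PLWD sex, relationship, caregiver age, caregiver sex, education: 8 | Gender and age, person not stated |
| Baseline burden | Not listed | Covariate |

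**3. Why baseline handling matters.** Let r be the baseline-to-follow-up correlation (not in the documents). Take equal variances and ignore other covariates. The standard error of the arm effect, relative to the raw-score comparison, is:
- baseline as covariate: sqrt(1 - r^2), which is 0.917 at r = 0.4 and 0.714 at r = 0.7;
- change score: sqrt(2(1 - r)), which is 1.095 at r = 0.4 and 0.775 at r = 0.7.

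So the raw-score standard error exceeds the baseline-adjusted one by 9% at r = 0.4 (1/0.917) and 40% at r = 0.7 (1/0.714). The change-score excess is 20% (1.095/0.917) and 8% (0.775/0.714). With 45 dyads per arm (half of the 90 expected at 6 months in protocol 7.1) and d = 0.65, normal-approximation power is 86.9% without baseline. With it, power is 94.5% at r = 0.5 and 99.1% at r = 0.7.

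**4. Simulation of both models on the same data.** There were 16,000 trials per cell. Assumptions not in the documents: 90 dyads with complete 8-week data, r = 0.4-0.7, DSRS-burden correlation 0.3, 55% spouses (not prognostic), education on 2 df, blocks of 4. The SAP model is read with caregiver age and sex. The protocol GEE uses both follow-ups with arm-by-time terms and an uncorrected sandwich with normal quantiles.

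| | r=0.4 | r=0.5 | r=0.6 | r=0.7 |
|---|---|---|---|---|
| Disagree on p<0.05 at d=0.65, raw score | 7.4% | 8.2% | 9.5% | 10.8% |
| Same, change score | 14.5% | 9.9% | 6.1% | 2.0% |
| No effect, either model significant, raw score | 8.6% | 9.0% | 9.0% | 9.9% |
| Same, change score | 8.9% | 8.8% | 8.7% | 8.3% |

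Repeat simulations with slightly different set-ups, including a corrected sandwich, widen the disagreement to about 7-13% (raw) and 2-16% (change).

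Some of the null excess is not due to the open choice. The SAP model alone gives 4.9-5.2%. The protocol GEE alone gives 6.5-6.7% uncorrected and 4.8-5.1% with a small-sample correction and t reference. With the correction, the either-model rate is 7.5-8.5% (raw) and 7.1-7.8% (change), about 7-9% across the runs.

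The gap between the SAP and raw-score estimates has a median of 0.07-0.11 SD. In one trial in ten it is at least 0.175-0.255 SD, which is 27-39% of 0.65 (0.175/0.65 and 0.255/0.65).

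**5. Which difference drives this.** Adding baseline burden to the protocol GEE, with a corrected sandwich, cuts its disagreement at d = 0.65 with a single baseline-adjusted OLS model to 0.9-4.4%. Reading gender and age as the caregiver's rather than the PLWD's changes p<0.05 in only 0.5-2.5% of trials. Independence and exchangeable working correlations gave identical 8-week results in all five complete data sets compared.

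**The case against.** *The SAP is the dedicated analysis document and governs by convention.* That is plausible, but no document says so. It would not settle the matter either, because the SAP gives no subscale, no time point and no owner for gender and age.

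*GEE and OLS are the same thing here.* This largely stands. At one time point with complete data and an identity link they coincide. A reader might infer from the two method names that the documents clash on the estimator; the conflict that remains without that is the covariates and baseline.

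*Protocol 3.1 says change, so baseline is in.* A reader might equally infer that the protocol ignores baseline altogether. Neither follows. H1 speaks of levels, and the allowance in 7.2.6 for correlation within person could take baseline as a repeated observation. None of these readings equals the SAP's baseline covariate. Under the repeated-baseline reading, disagreement at d = 0.65 is 1.5-13.5%.

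*Both are valid prespecified adjustments in a randomised trial.* This stands for bias, and for type I error once the sandwich is corrected. It does not say which result is primary.

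*The false-positive rates are a worst case.* This stands. They require both models to be run and the more favourable one reported, and the documents plan nothing of the kind.

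**Conclusion.** The concern holds as a contradiction between the two documents on covariates and baseline handling, compounded by an outcome definition that is not aligned. The public text gives no precedence; front-matter pages missing from it could not be checked.

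At d = 0.65 the choice of document changes p<0.05 in roughly 7-13% of trials (raw score) or 2-16% (change score). Omitting baseline from a raw-score model loses precision. If the more favourable model were reported, the false-positive rate could rise to about 7-9% corrected, or 8-10% uncorrected. All of this rests on the assumed correlations, 90 dyads and complete 8-week data. Missing data, which both documents plan for, were not simulated.

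A reader might infer that the trial's type I error already exceeds 5%, or that the sponsor means to choose between results. The documents support neither: one corrected model used alone stays near 5%, and nothing suggests selective reporting. The point should be corrected before analysis, but it does not invalidate the design.

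**What to change.** Put one identical statement in protocol 7.2.6 and in the SAP (predictors and analytic approach) that names:
- the governing primary model;
- the RMBPC Disruption score at each stated time point as the outcome;
- the baseline Disruption score as a covariate;
- the full covariate list, saying whose age and sex.

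One example is OLS with robust standard errors on arm, baseline Disruption score, caregiver age, caregiver sex and spouse/non-spouse. The last three are the factors named in protocol 5.3.1. This model stands in neither document as written; another would serve if it is fully stated and includes baseline. Label the other model a sensitivity analysis, with baseline Disruption score added and a small-sample-corrected sandwich with a t reference.

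The cost is wording. All variables are already planned for collection and the sample size does not change. Under the example, spouse status takes one degree of freedom, at most 0.6 power points if it is not prognostic. How the 5% is shared between 8 weeks and 6 months, and whether the randomisation blocks are stratified, are separate questions and not part of this change.
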